5.4.2.3 Clinical Quantitative Endpoints Analysis

For quantitative endpoints, the average of the values obtained by at least 3 cardiologists on the experts' exams will be considered as the reference value. Similarly, the average of the values obtained by at least 3 cardiologists on the novices' exams will be considered as the tested value.

The following metrics will be computed for each endpoint:

- The number and proportion of novices' and experts' exams on which at least 3 cardiologists were able to make the quantitative assessment.
- The mean and standard deviation of the distribution of the reference and tested values.
- The mean, standard deviation, and 95% CI of the difference will be calculated between the measurements made on the acquisitions obtained by the novices and those obtained by the experts.
- The concordance of measurements will be assessed using the intraclass correlation coefficient (ICC), and its 95% CI.
- The Pearson or Spearman correlation coefficient will be computed depending on the distribution.
- Bland-Altman and correlation plots will be performed.

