2.1 Study Design

This prospective multicentric international non-inferiority pivotal investigation will evaluate the ability of the Heartfocus software to support novices for the acquisition of 10 reference views of cardiac ultrasound. The 10 reference views are the following:

- apical 2-chamber (A2C),
- apical 3-chamber (A3C),
- apical 4-chamber (A4C),
- apical 5-chamber (A5C),
- parasternal long axis (PLAX),
- parasternal short axis at the aortic valve (PSAX-AV),
- parasternal short axis at the mitral valve (PSAX-MV),
- parasternal short axis at the papillary muscles (PSAX-PM),
- subcostal 4-chamber (SC-4C),
- subcostal inferior vena cava (SC-IVC).

Novices will be nurses without prior ultrasound experience who have received dedicated training on cardiac ultrasound and Heartfocus software.

Patients included in the study will be adult patients scheduled for an echocardiogram at one of the two investigating centers. Each patient included in the study will receive a standard cardiac ultrasound exam performed in the standard way with the regular ultrasound system used in the cardiologic service.

Patients will receive 2 additional limited exams to their standard exam, which consist of the acquisition of ultrasound clips for each of the 10 reference views:

- one by a novice, *i.e.* nurses having received a dedicated training of 2 days, with the Clarius phased array probe and the HeartFocus software with the guidance system,
- one by an expert (experienced sonographer cardiologist) with the Clarius phased array probe and the HeartFocus software without the guidance system.

A total of 8 novices will perform the acquisition on 30 different patients each. In total 240 patients will be included in the analysis, half in each investigator center. The exams (240 acquired by novices, 240 by experts) will be assessed by an independent review committee, composed of 5 different cardiologists. Each exam will be reviewed by all 5 cardiologists from this committee. Cardiologists will not know if the exam was performed by a novice or an expert. Cardiologists will be blinded to the investigating center in which the acquisition has been performed.

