2.2 Collected Data

The following data will be collected for both the exam acquired by the expert and the exam acquired by the novice:

- Whether the exam was acquired by the expert/novice,
- Reason for not acquiring the exam,
- Whether the exam has successfully been exported for review by the cardiologists,
- Number of clips acquired by the expert/novice,
- Novice acquisition duration in minutes,
- Report of Adverse event (AE) with details, start and end date, severity, relationship, action taken and outcome,
- Report of Device deficiency (DD) with details, date, type, and reason of deficiency, action taken and outcome,
- Report of Serious adverse event (SAE) with details, start and end date, severity, relationship, action taken, and outcome.

The following data will be collected for each review performed by each cardiologist on each exam for qualitative assessment:

- Qualitative assessments
- For the 10 reference views of cardiac ultrasound (PLAX, PSAX-PM, PSAX-MV, PSAX-AV, A4C, A5C, A2C, A3C, SC-4C and SC-IVC), quality of diagnostic (Yes/No/No clip),
- Qualitative visual assessment of left ventricular size (Yes/No) and type* (if Yes),
- Qualitative visual assessment of left ventricular function (Yes/No) and type* (if Yes),
- Qualitative visual assessment of right ventricular size (Yes/No) and type* (if Yes),
- Qualitative visual assessment of right ventricular function (Yes/No) and type* (if Yes),
- Qualitative visual assessment of non-trivial pericardial effusion (Yes/No) and type* (if Yes),
- Qualitative visual assessment of left atrial size (Yes/No) and type* (if Yes),
- Qualitative visual assessment of right atrial size (Yes/No) and type* (if Yes),
- Qualitative visual assessment of segmental kinetics of the left ventricle (Yes/No) and type* (if Yes),
- Qualitative visual assessment of aortic valve (Yes/No) and type* (if Yes),
- Qualitative visual assessment of mitral valve (Yes/No) and type* (if Yes),
- Qualitative visual assessment of tricuspid valve (Yes/No) and type* (if Yes),
- Qualitative visual assessment of inferior vena cava size (Yes/No) and type* (if Yes).

* For each assessment, the type will be described in section 3.4.1.

The following data will be collected for each review performed by each cardiologist on each exam for quantitative assessment:

- For PLAX clip:
 - If measurement = Yes, IVSd, LVEDD, and PWd measurement (in mm),
 - If measurement = Yes, LVESD measurement (in mm),

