 - If measurement = Yes, Aortic root measurement (in mm),
- For A4C clip:
 - If measurement = Yes, A4C single-plane LV EDV and LV ESV measurement (in mL) and LV EF measurement (in %),
- For A2C clip:
 - If measurement = Yes, A2C single-plane LV EDV and LV ESV measurement (in mL), LV EF measurement (in %),
- For A4C and A2C clips:
 - If measurement = Yes, Biplane LV EDV and LV ESV measurement (in mL) and Biplane LV EF measurement (in %),
- For SC-IVC clip:
 - If measurement = Yes, Diameter of the IVC measurement (in mm).

The following data will be collected for each patient:

- Information regarding consent form and eligibility criteria,
- Information regarding premature discontinuation (date of end of study and reason for study exit),
- Demographics (age, sex, height, weight, BMI, ethnicity*, race*),
- Indication for cardiac ultrasound exam,
- Prior cardiac diagnoses (hypertension, hyperlipidemia, diabetes, heart failure, atrial fibrillation, other arrhythmias, coronary artery disease, prior heart attack, valvular heart disease, pulmonary hypertension, heart transplant, cardiomyopathies, congenital heart disease, other and specification of other prior cardiac diagnoses, none, not reported),
- Prior non-cardiac diagnoses (renal disease, COPD/emphysema, pulmonary embolus, systemic infiltrative disease like amyloid or hemochromatosis, cancer, underwent chemotherapy, underwent radiation, other and specification of other prior non-cardiac diagnoses, none, not reported),
- Implanted medical devices (pacemaker/ICD, leadless pacemaker, prosthetic heart valve, LAA closure device, atrial septal defect closure device, ventricular septal defect closure device, patent foramen ovale closure device, valve repair device, other and specification of other implanted medical devices, none, not reported),
- Cardiac abnormalities (abnormal left ventricular size or function, abnormal right ventricular size or function, abnormal left atrial size, abnormal right atrial size, septal defect, abnormal mitral valve, abnormal tricuspid valve, abnormal aortic valve, non-trivial pericardial effusion, abnormal inferior vena cava size, patent foramen ovale, other and specification of other cardiac abnormalities, none, not reported).

* Only collected for US patients.

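### Quantitative novice and expert values are averaged over whichever 3 to 5 cardiologists measured each exam, so reader offsets can enter the difference; a reader-adjusted analysis would remove them cheaply

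*SAP*

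**What the plan says.** SAP 5.4.2.3 defines the two values separately, each as "the average of the values obtained by at least 3 cardiologists on the" exam concerned. For the reference, "the average of the values obtained by at least 3 cardiologists on the experts' exams will be considered as the reference value". For the comparison, "the average of the values obtained by at least 3 cardiologists on the novices' exams will be considered as the tested value". The section then states: "The mean, standard deviation, and 95% CI of the difference will be calculated between the measurements" on novice and expert acquisitions. It adds the ICC, a correlation coefficient and Bland-Altman plots.

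Five readers are available for every exam (SAP 2.1: "Each exam will be reviewed by all 5 cardiologists from this committee"), but each records a number only if they chose to measure. In SAP 2.2 the entry for the parasternal long-axis clip begins "If measurement = Yes, IVSd, LVEDD, and PWd measurement (in mm", and the other quantitative items carry the same condition. Fewer than five values is foreseen, because SAP 5.4.2.3 plans to report this: "The number and proportion of novices' and experts' exams on which at least 3 cardiologists were able to make the quantitative assessment".

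SAP 4.3 leaves missing values unreplaced. The pairing rule in SAP 4.2.3 concerns patients with both exams, not readers. Multi-reader multi-case methods are named only for the primary and quality proportions (SAP 5.4.1 and 5.4.2.1). SAP 5.5.2 estimates differences between pairs of readers but does not carry them into the novice-expert comparison.

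**The concern.** The secondary objective is agreement between novice and expert acquisitions, so the difference should reflect who acquired the images. Under the stated rule it also reflects who measured them. If one cardiologist traces volumes generously and measures the expert exam but not the novice exam, the patient's difference shifts for a reason unrelated to the novice.

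Two consequences need to be kept apart. Random mismatch adds noise to the SD, the limits of agreement and the ICC. Systematic mismatch moves the mean difference, and a larger sample does not remove that.

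**Working it through.** The plan gives no SD, margin or power for the quantitative endpoints, so there is no figure of its own to reproduce.

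**Inputs from the documents.** 240 patients, 5 readers, at least 3 values per exam, no imputation.

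**Inputs assumed.** Reader-offset SD s = 3 to 5 units (for example ejection-fraction points); reader error SD 5; acquisition SD 3; measuring rates per reader of 95% on expert and 80% on novice exams, or 90% and 70%.

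**Step 1: offset left in one patient's difference.** Let a and b be the numbers of readers on the two exams and c the number in common. The offset variance is s² × (1/a + 1/b − 2c/(ab)).

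| Readers | Common | SD of artefact | s = 3 | s = 5 |
|---|---|---|---|---|
| 5 and 5, or any identical sets | all | 0 | 0 | 0 |
| 4 and 5 | 4 | 0.224 s | 0.7 | 1.1 |
| 3 and 5 | 3 | 0.365 s | 1.1 | 1.8 |
| 3 and 3 | 1 | 0.667 s | 2.0 | 3.3 |

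The last row is the worst case, since two sets of 3 out of 5 must share at least 3 + 3 − 5 = 1 reader.

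**Step 2: effect on the SD of the difference when declining is unrelated to reader.** Let h(p) be the mean of 1/k over the number k of readers who measure, given k ≥ 3, when each measures with probability p. From the binomial distribution, h(0.95) = 0.2131, h(0.80) = 0.2507, h(0.90) = 0.2263 and h(0.70) = 0.2707. The mean of c given a and b is ab/5, so

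variance = 3² + 5² × (h₁ + h₂) + s² × (h₁ + h₂ − 2/5).

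- Rates 95%/80%: h₁ + h₂ = 0.4638. With s = 0 the SD is √20.59 = 4.54. With s = 3, 4, 5 it is √21.17 = 4.60, √21.61 = 4.65, √22.19 = 4.71, an increase of 1.4% to 3.8%.
- Rates 90%/70%: h₁ + h₂ = 0.4970. With s = 0 the SD is √21.43 = 4.63. With s = 3 and 5 it is √22.30 = 4.72 and √23.85 = 4.88, an increase of 2.0% to 5.5%. This takes roots of averaged variances, which slightly overstates the average SD.

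Simulation under the same assumptions gave 4.61, 4.65 and 4.70 in the first case, with a mean difference of about 0. Only about 29% of usable pairs there had identical reader sets.

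**Step 3: when the mean is biased.** Suppose two of the five readers read g units higher and measure 50% of novice exams, with all other rates 95%. The high readers' average share of an expert value is 2/5 = 0.400. Their share of a novice value, given at least 3 readers, is 0.2336/0.9607 = 0.243. The bias is g × (0.243 − 0.400) = −0.157 g, which is −0.31, −0.63 and −0.94 for g = 2, 4, 6. Simulation gave −0.33, −0.62 and −1.00. For scale, with a simulated SD of 4.60 and about 230 usable patients, the 95% CI half-width is 1.96 × 4.60/√230 = 0.59.

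**Step 4: would restricting to common readers help?** Offsets then cancel exactly, but readings are lost. At 95%/80% a reader measures both exams with probability 0.95 × 0.80 = 0.76, and h(0.76) = 0.2593. The SD is √(9 + 2 × 25 × 0.2593) = 4.69 whatever s is. That is above the SAP rule at s = 3 (4.60) and s = 4 (4.65), and only just below it at s = 5 (4.71). Usable patients fall from about 226 to 217; at 90%/70% they fall from about 199 to 176.

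**Step 5: adjusting for reader and keeping all values.** With up to 240 × 2 × 5 = 2,400 measurements the five reader effects are well estimated. The s² term in Step 2 then essentially disappears, leaving an SD near 4.54 with no patients lost. The bias in Step 3 also goes.

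**The case against.** The strongest reply is that nothing decisive depends on this. The quantitative comparison has no margin or acceptance limit, the only success criterion concerns the four primary proportions (SAP 3.3), and SAP 5.5.2 will show each reader pair's mean difference on novice and on expert exams, so large offsets would be visible. All of that stands, and it limits the weight of the point. Visible offsets are still not removed from the comparison.

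Three stronger readings are tempting, and the documents do not support them.

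- A reader might infer that the rule biases the mean difference as it stands. It does so only if two things coincide: a reader measures systematically high or low, and that reader's measuring rate changes between expert and novice exams differently from the others'. Being strict about image quality is not itself a measurement offset. SAP 2.2 shows only that measuring is optional, not that readers decline more often on novice exams.
- A reader might take the 1.8 or 3.3 units of Step 1 as the widening of the reported limits. They are one component of a single patient's difference, the larger is the worst case, and both use the top of the assumed range. Combined with the other variation, the widening is a few per cent.
- A reader might conclude that only readers common to both exams should be used. Step 4 shows that this costs patients and does not lower the SD over most of the assumed range. If poorer exams are measured less often, the patients lost would be mainly those.

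**Conclusion.** The point holds in a limited form. SAP 5.4.2.3 lets reader offsets into the novice-expert difference whenever a patient's two exams were measured by different sets of cardiologists, and no other section corrects for this. Under random declining the consequence is an SD and limits of agreement wider by about 1% to 5%, with an unbiased mean. Under selective declining by readers who also have an offset, the mean shifts: about -0.3 to -1 unit in the illustrative case, which can be as large as the half-width of its confidence interval.

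These sizes rest on assumed offsets, error SDs and measuring rates, and would change with them. If all five readers measure both exams, the effect is zero. Only secondary descriptive endpoints are involved.

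**What to change.** Revise SAP 5.4.2.3 as follows.

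- **Mean difference and its 95% CI:** fit a mixed model to the individual reader measurements, with effects for operator (novice or expert) and reader, and random effects for patient and for exam within patient.
- **SD, Bland-Altman and ICC:** subtract the estimated reader effect from each measurement, then average per exam where at least 3 readers measured. Each patient keeps two values, which the ICC and the Bland-Altman horizontal axis both need; a within-reader difference alone would supply neither.
- **Sensitivity analysis:** report the within-reader novice-minus-expert difference averaged over common readers, with the number of patients who have fewer than 3 common readers.

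The measurements are already collected by cardiologist and exam (SAP 2.2). The protocol's analysis section asks for the mean, SD and CI of the difference without prescribing how readers are averaged, so it need not change. The cost is some extra analysis work and reliance on an additive reader effect: a reader whose offset itself varies with image quality would not be fully corrected. This is a cheap improvement.

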5.4.2.4 Duration Endpoint Analysis

A quantitative analysis will be performed for the duration endpoint.

5.5 Other Analyses

5.5.1 Intra-Observer Study

The purpose of the intra-observer study is to check the reproducibility of a review by the same cardiologist. The intra-observer study will be performed randomly on 10% of the exams from the FAS population. A balance between experts' and novices' exams and between both centers will be performed. 2 reviews of the same exam, at least 3 weeks apart, will be performed by each cardiologist. No comparisons will be made between the novices' exams and the experts' exams.

For each cardiologist and all 5 cardiologists together, the agreement rate and the intraclass correlation coefficient (ICC) with their 95% CI will be computed for qualitative (primary, quality, and clinical qualitative) and quantitative (clinical quantitative) endpoints respectively, on the 10% of exams between the first and second review.

Those comparisons will be made for each cardiologist to evaluate individually if the cardiologist makes reproducible reviews, and for all 5 cardiologists together to evaluate globally if the 5 cardiologists make reproducible reviews.

5.5.2 Inter-Observer Study

The purpose of the inter-observer study is to check the reproducibility of a review by different cardiologists. The inter-observer study will be performed twice, in the FAS population:

- on novices' exams,
- on experts' exams.

For each qualitative (primary, quality, and clinical qualitative) endpoint:

- The number and proportion of exams where at least 3, 4, and 5 cardiologists agree will be computed.
- The agreement between each pair of cardiologists will be assessed using the agreement rate, and its 95% CI.

For each quantitative (clinical quantitative) endpoint:

- The mean, standard deviation, and 95% CI of the difference between the assessments of each pair of cardiologists will be calculated.
- The concordance of measurements will be assessed using the ICC, and its 95% CI.

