3.5 Sample Size Justification

The main hypothesis for the sample size calculation is based on the sequential testing of the four primary endpoints (the left ventricular size, the left ventricular function, the size of the right ventricle, and the presence of non-trivial pericardial effusion) with the performance goal of 80% (each lower 2-sided 95% CI limit for each parameter should be greater than 80%).

As the study design is like the pivotal trial, conducted by a US team, which led to FDA certification of our competitor software to assist novices in performing cardiac ultrasound acquisitions, we based our sample size calculation on the sample size calculation of the pivotal trial. This pivotal trial included 240 patients and 8 different operators. Each operator performed the acquisitions on 30 patients.

The elements for the sample size calculation of the pivotal study are described below:

- the pivotal study was powered to detect the primary endpoint's exceeding the performance goal of 80% ($\alpha = 0.05$, $\beta = 0.2$),
- the statistical power was estimated using iMRMC 4.0 software developed by the FDA, which provides the 95% CI around the point estimate for a given parameter and was used for the primary endpoint analysis,
- the sample size (240 patients and 8 different operators who performed the acquisitions on 30 patients) would have a statistical power of 0.98 for each parameter or greater than 0.92 for 4 sequentially tested parameters.

4. Statistical Methodology

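### For yes/no items the SAP checks reader reproducibility with raw-agreement statistics only, which say little about whether readers flag the same inadequate exams when most answers are 'yes'

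*SAP*

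**What the plan says.** SAP 2.1 has all five committee cardiologists read every exam ("Each exam will be reviewed by all 5 cardiologists from this committee"), with 240 novice and 240 expert exams planned.

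SAP 5.5.2 states its aim: "The purpose of the inter-observer study is to check the reproducibility of a review by different cardiologists". It is run once on novices' exams and once on experts' exams. For qualitative endpoints, including the four primary ones, it lists two outputs:

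- for readers taken two at a time: "The agreement between each pair of cardiologists will be assessed using the agreement rate, and its 95% CI"
- for the panel as a whole: "The number and proportion of exams where at least 3, 4, and 5 cardiologists agree will be computed"

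SAP 5.5.1 covers repeat reviews by the same cardiologist on 10% of exams. There "the agreement rate and the intraclass correlation coefficient (ICC) with their 95% CI will be computed for qualitative (primary, quality, and clinical qualitative) and quantitative" endpoints respectively, so the agreement rate belongs to the qualitative items and the ICC to the measurements. Results are given per cardiologist and for all five together.

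Neither document mentions kappa or another chance-corrected index, agreement split by 'yes' and 'no', agreement expected by chance, or a level of agreement that would count as acceptable. Both sections sit under SAP 5.5, Other Analyses.

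**The concern.** Raw agreement mixes two things: how consistently readers judge the same exam, and how lopsided the answers are. When nearly everyone answers 'yes' to nearly every exam, two readers agree often even if their few 'no' answers fall on different exams.

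Lopsided answers are what the trial hopes for. The success rule in SAP 3.5 is that "each lower 2-sided 95% CI limit for each parameter should be greater than 80"%, and patients whose earlier reports mention poor echogenicity are excluded. The informative exams are those that at least one reader calls inadequate, and raw agreement gives them little weight.

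What is at stake is the meaning of the reproducibility section. A report could show agreement above 90% and be read as evidence that the committee reliably recognises inadequate exams, which that figure cannot show. Because 5.5.2 is run separately by operator type, agreement could also look better on expert exams only because they attract more 'yes' answers.

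**Working it through.** **Inputs from the documents.** Five readers per exam; 240 novice and 240 expert exams (SAP 2.1); a 10% sample for repeat reviews (SAP 5.5.1); a performance goal of 80% (SAP 3.3 and 3.5).

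**Assumption.** The per-reader 'yes' rate p is not stated. A range of 80% to 98% is used.

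**Plan's own figure.** There is none for agreement. The nearest stated figure is power, taken from another trial's calculation: 0.98 per parameter and above 0.92 for four. It reproduces, since 0.98^4 = 0.922. With a simple exact interval and no reader variance, 205/240 (85.4%) is the smallest count whose lower limit exceeds 80%, and power is 0.981 at a true rate of 89.5%. This is only a loose guide to p, because SAP 5.4.1 counts majority-of-five results and not single readings.

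**Step 1: pairwise agreement by chance.** For two independent readers with the same 'yes' rate, Pe = p² + (1 − p)².

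| Assumed 'yes' rate | Pe |
|---|---|
| 80% | 0.64 + 0.04 = 0.680 |
| 90% | 0.81 + 0.01 = 0.820 |
| 95% | 0.9025 + 0.0025 = 0.905 |
| 98% | 0.9604 + 0.0004 = 0.961 |

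At 89.5%, Pe is about 0.81. Unequal reader rates averaging 95% (97/93 to 99/91) give 0.904 to 0.902, so the equal-rate assumption matters little.

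**Step 2: the 3/4/5-reader counts.** Five answers to a binary item always contain at least three alike, so the first count is 100% whenever all five answer. For five independent readers at p = 0.95:

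- All five agree: 0.95^5 + 0.05^5 = 0.774.
- At least four agree: 0.774 + 5 × 0.95^4 × 0.05 + 5 × 0.05^4 × 0.95 = 0.977.

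At p = 0.80 the same formulas give 0.328 and 0.744. These counts depend on prevalence just as the pairwise rate does.

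**Step 3: what one raw rate can mean.** Take 92% observed agreement, so 8% of exams are discordant, and equal reader rates. The joint 'no' share is p00 = (1 − p) − 0.04. Negative agreement is 2·p00/(2·p00 + 0.08).

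| 'Yes' rate | p00 | Negative agreement | Value under independence (1 − p) |
|---|---|---|---|
| 80% | 0.16 | 0.32/0.40 = 80% | 20% |
| 90% | 0.06 | 0.12/0.20 = 60% | 10% |
| 95% | 0.01 | 0.02/0.10 = 20% | 5% |

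Positive agreement stays near 95–96% in all three rows. At 95% 'yes' it is 1.82/1.90 = 95.8%, against 95% under independence. The raw rate is the same throughout, while agreement on inadequate exams ranges from good to poor.

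**Step 4: novice against expert.** If novice exams drew 90% 'yes' and expert exams 98% (assumed), chance agreement alone would be 82% against 96.1%, a gap of about 14 points with no difference in reader consistency.

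**Step 5: how much information is there on 'no'?** At 95% 'yes':

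- 5.5.2: 240 × 0.05 = 12 'no' readings per reader. In the 92% example, 240 × 0.01 = 2.4 exams per pair are called 'no' by both. Sampling variation then puts the estimate for a single pair between 0% and about 42% (true value 20%).
- 5.5.1: 10% of 480 is 48 exams, so 48 × 0.05 = 2.4 'no' readings per cardiologist per review. If 92% agreement also held between the two reviews, the chance of no exam being called 'no' twice is 0.99^48 = 0.62. Pooled over five cardiologists there are about 12 'no' readings per review.

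**The case against.** Pairwise agreement with a confidence interval is a legitimate and transparent description, and the SAP contains no error or contradiction here. Specific agreement could be computed later from the same readings. That is fair, and it is why this is an improvement rather than a defect.

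The proposed statistics also have limits. Positive agreement depends on prevalence as raw agreement does, and negative agreement is not chance-corrected, so 20% should be read against its 5% baseline. For a single pair, and still more for a single cardiologist in 5.5.1, negative agreement would be very imprecise. This stands, and it shapes the fix: show the baseline and the counts, and pool in 5.5.1.

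A reader might infer several stronger points that the documents do not support:

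- That the pairwise rate is the only statistic. SAP 5.5.2 also lists the 3/4/5-reader counts, although these are raw agreement as well.
- That chance agreement will be about 90%. This needs a 95% 'yes' rate, which appears nowhere in the documents. A trial that only just met its criterion at 205/240 could have a lower rate; at 85.4% 'yes', chance agreement is 75%.
- That the readers would pass the check however they performed. Neither section sets a threshold or a decision.
- That the primary result is affected. No agreement figure enters the criterion in SAP 3.3, and the primary interval comes from the MRMC analysis in SAP 5.4.1.

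**Conclusion.** The point holds as a limited one. For yes/no items, SAP 5.5.1 and 5.5.2 rely on raw agreement alone, and one of the listed counts carries no information for a binary item that all five readers answer. Depending on the unstated 'yes' rate, independent readers would agree 68% to 96.1% of the time over an assumed range of 80% to 98%. The weakness is modest at the low end and severe at the high end. A high rate would not show that readers recognise the same inadequate exams, and a difference between the novice and expert rates could reflect prevalence alone.

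The figures assume independent readers with a common 'yes' rate. The conclusion that raw agreement moves with prevalence does not depend on any particular rate. The effect is confined to what the reproducibility sections can support; no primary or secondary endpoint result would change.

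**What to change.** In SAP 5.5.2, for each yes/no item and separately for novice and expert exams, add beside the raw rate:

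- positive specific agreement, 2·p11/(2·p11 + discordant), and negative specific agreement, 2·p00/(2·p00 + discordant), where p11 and p00 are the shares of exams called 'yes' by both readers and 'no' by both;
- the number of 'no' readings behind the negative figure;
- the values expected under independence, which for two readers with the same rates are the 'yes' rate and the 'no' rate (for example 95% and 5%);
- confidence intervals clustered by exam for any figure pooled over the ten reader pairs.

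In SAP 5.5.1, report the two specific-agreement figures pooled over the five cardiologists only, with counts and intervals clustered by exam. Keep the planned per-cardiologist raw rates.

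Specific agreement is suggested rather than kappa because kappa is itself unstable at extreme prevalence.

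Cost: two more figures per item from readings already collected, with no new reviews and no change to any endpoint. The negative figure will be imprecise and may look unfavourable. This is a cheap improvement.
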